2.2.2 Known Potential Benefits

MRI

Immediate potential benefits

- There is no immediate potential benefit.

Long-range potential benefits

- Screening the brain with an MR allows us to investigate potential changes due to the rTMS treatment. Detecting these often subtle changes provides an objective measure of the effects of the treatment on the brain's structural and functional properties. To evaluate the outcome of the treatment, MRI data is an essential tool.
Also, the screening of the brain has the potential benefit of detecting abnormalities that might have otherwise been missed.

rTMS and AVH symptomatology

Immediate potential benefits

- The known immediate potential benefits include reduced severity of auditory verbal hallucinations immediately after the treatment.

Long-range potential benefits

- In schizophrenia, Hoffman et al. (1999) were the first to introduce rTMS for the treatment of refractory AVH in treatment-resistant patients. The authors used LF rTMS over the left temporo-parietal junction (TPJ) and showed significantly reduced AVH severity with effects lasting up to 15 weeks. Following this promising result, several studies replicated these findings (Brunelin et al., 2006; Chibbaro et al., 2005; Hoffman et al., 2000; Hoffman et al., 2005; Hoffman et al., 2007; Jandl et al., 2006; Klirova et al., 2013; Lee et al., 2005; Poulet et al., 2005; Vercammen et al., 2009).

2.2.3 ASSESSMENT OF POTENTIAL RISKS AND BENEFITS

MRI

The MRI measurement on the one hand constitutes of a minimal risk. On the other hand, analyzing the MR data does not only allow assessing the effects of rTMS on an objective, physiological level, but allows the clinical assessment of the brain physiology regarding preexisting anomalies and potential treatment-related changes. It is therefore crucial as a diagnostic and outcome measure.

rTMS & AVH symptomatology

Up to 70% of schizophrenia patients suffer from auditory verbal hallucinations (AVH), one of the cardinal symptoms of schizophrenia. Yet, in about 20-30% of patients even extended antipsychotic medication does not ameliorate AVH (Waters, 2012) and is often accompanied by side effects. Thus, new therapeutic options are needed. Studies using low-frequency rTMS over the left temporo-parietal junction have shown medium to large effect sizes. These results indicate that rTMS might be a promising option in the treatment of AVH. Therefore, it is vital to explore the effects of rTMS in medication-free individuals in the initial phase of psychosis and, secondly, to use an accelerated protocol of multiple rTMS-sessions within a short period of time. The reduced time of rTMS administration would diminish potential risks related to other psychotic symptoms and reveal rTMS effects on AVH within a few days. The considerable potential benefit for participating patients, especially for those in the treatment arm, outweighs the potential minimal side effects of a headache or itching phe at the side of stimulation. Further, the likelihood of seizures is very small, considering a low-frequency stimulation intensity.

3 OBJECTIVES AND ENDPOINTS

OBJECTIVES	ENDPOINTS	JUSTIFICATION FOR ENDPOINTS
Primary		
Examine the efficacy of low-frequency rTMS for the treatment of AVH in patients with a schizophrenia spectrum disorder.	Our primary outcome will be the score of the Hallucination Change Scale (HCS) (Hoffman et al., 2003). Response criteria: a) Clinically significant improvement in AVH is	The HCS is used as our primary outcome measure. The scale will be anchored at baseline using the narrative description of AVHs provided by the patient for the prior 24 hours, which will be assigned a score of 10. For subsequent assessments, the HCS ranges from 0-20 (with a score of 20

OBJECTIVES	ENDPOINTS	JUSTIFICATION FOR ENDPOINTS
	defined as a score of <8 on the HCS (Hoffman et al., 2013) b) Drop-outs: defined as patients who discontinue treatment before completing the 4 rTMS sessions.	corresponding to hallucinations twice as severe as baseline) (Hoffman et al., 2003; Hoffman et al., 2013). The HCS is a frequently used assessment for AVH in schizophrenia (Hoffman et al., 2003; Hoffman et al., 2013; Philipp Homan et al., 2011; P Homan et al., 2012). It is a feasible and time-efficient measure to assess severity of AVH on a daily basis and to evaluate improvement of AVH severity.
Secondary		
Monitor qualitative changes in AVH during the course of the rTMS treatment.	a) the qualitative content of AVH are assessed using the BAVQ-R to monitor changes in the content of AVH.	The BAVQ-R (CHADWICK, LEES, & BIRCHWOOD, 2000) is a self-report measure of patient's beliefs, emotions and behavior about AVH. This allows to assess changes in the quality of AVH over time and monitor if severity increases to the point of being dangerous for the patient or others (suicidal or homicidal tendencies).
Assessment of AVH as part of positive symptoms.	b) positive symptoms BPRS-subscale including "Hallucinatory Behavior", "Conceptual Disorganization", "Suspiciousness", and "Unusual Thought Content".	The positive symptoms BPRS-subscale is a well validated, often in studies used measure to assess positive symptoms including AVH (Robinson et al., 2015; Shafer, 2005).
Examine the effects of rTMS on the global functioning of the patient with a schizophrenia spectrum disorder.	c) global function is assessed using the Clinical Global Impression (CGI) and the General Assessment of Functioning (GAF)	The global scores (CGI (Haro et al., 2003) and GAF (Jones, Thornicroft, Coffey, & Dunn, 1995)) nicely complement the specific measure and provide a complete picture of the patient's mental state.
Confirm that rTMS has no cognitive side effects.	d) The neuropsychological test Repeatable Battery for the Assessment of Neuropsychological Status (rBANS)	In order to confirm that rTMS has no undesirable cognitive side effects the rBANS is used as a standard cognitive measure.

Neurophysiological changes using magnetic resonance imaging (MRI) are investigated as predictors for rTMS treatment response.

4 STUDY DESIGN

4.1 OVERALL DESIGN

This is a randomized, placebo controlled, double-blind clinical trial. We aim to assess the efficacy of rTMS as a potentially beneficial treatment option in drug-naïve patients and patients refusing antipsychotic medication who suffer from AVH. We use a novel protocol with only one day of treatment including 4 sessions of low-frequency rTMS and compare the effects with the sham stimulation. Further, we aim to examine structural and functional neurophysiological characteristics as predictors for rTMS.

As primary outcome, we aim to examine the efficacy of low-frequency rTMS for AVH in patients with a schizophrenia spectrum disorder with regard to AVH based on the HCS. Further, Hallucination quality (BAVQ-R), hallucinations as a part of positive symptoms (BPRS-subscale), clinical global improvement (CGI), and general assessment of functioning (GAF) are secondary outcome measures. Structural and functional neurophysiological characteristics (rCBF, resting fMRI, T1, and DTI) are investigated as potential predictors for rTMS treatment response.

In order to achieve these aims, we will have two intervention arms: real and sham rTMS. Patients who are willing to take part in the study and declining treatment by antipsychotic medication to sufficiently treat psychotic symptoms will be randomly assigned by the (trained) research coordinator to either sham or real rTMS.

Subjects will be randomized using a permutation block design to real rTMS or sham rTMS treatment. Accordingly, a well-documented double-blind randomization plan will be developed by the study's biostatistician and implemented in collaboration with the investigator. Copies of the resulting permutation blocks and randomization codes will be kept by the unblinded research coordinator. Blinded study personnel will not have access to these codes. When a new subject is randomized to a particular group, the research coordinator will provide written notice of the randomization condition of the subject to the operator of the rTMS.

Double-blinding is ensured by the fact that the trained research assistant who is performing the rTMS treatments is not the same person (rater) who will conduct the psychopathology assessments. This allows the unbiased assessment of changes in AVH severity due to rTMS without the prior knowledge of the rater whether the patient received real or sham rTMS.

The treatment will be offered only if clinically indicated and the benefits of procedure outweigh risks. Therefore, participating in the study does not introduce additional risks to the patient other than the risks which are already present because of the clinical care.

rTMS is a non-invasive procedure with the most common side effect being headache or pain, which is transient and responds well to combination of acetaminophen and ibuprofen (we will administer if patients require so). If local scalp pain or face muscle pain occurs, adjustment of the coil usually alleviates the pain. There are no known mechanisms through which the induced magnetic field produced during TMS stimulation could generate biological adverse effects in the absence of extraneous implanted metal in the skull or brain. That is the reason we will exclude all patients with metal implants (they would not be eligible because of the MRI component either). The most significant safety concern is seizure, however, as can be seen from Table 3, 1Hz rTMS for 1800 seconds is considered safe (Rossi et al., 2009). As a safety precaution, however, we will exclude patients with seizure disorders from this study. There are no additional significant risks due to study procedures.

Recruitment will occur at the Zucker Hillside Hospital at Northwell Health. For further information on recruitment see section 5.5 "Strategies for Recruitment and Retention". Regarding data analyses, no interim analyses are scheduled at this point.

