4.2 SCIENTIFIC RATIONALE FOR STUDY DESIGN

We will obtain a blood sample to assess the serum concentration of the antipsychotic at the moment of hospitalization to confirm that patients are antipsychotic-free thus eligible for this study. In the event of not having obtained a blood sample in the emergency room for an eligible patient that is willing to consent due to logistic reasons, we will obtain the specimen via venipuncture after the consent form is signed, provided that the patient did not receive antipsychotic drugs in the emergency room or inpatient unit. The specimens of individuals for whom an extra vial of blood was extracted for potential serum antipsychotic concentration analysis that later do not consent to participate in the study will be destroyed immediately without being processed.

For TMS, it is important to at least have a group that gets treated with the sham rTMS if no cross-over trial is possible and no waiting-list is planned to be included in the study.

Having matched patients in the control group compared to the treatment group allows a comparison of the two in terms of symptoms. A healthy control group would not allow such a comparison.

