Recruitment will occur at The Zucker Hillside Hospital from the inpatient unit at Northwell Health. The Zucker Hillside Hospital is the major psychiatric facility associated with the health system. Subjects will be recruited from the inpatient and outpatient units. Prospective subjects will be approached for study enrollment by the psychiatrists who participate in this study and/or a research fellow. Upon subject's agreement, a meeting with the research staff will be scheduled to begin the informed consent process.

The consent process begins with an assessment of the patient's ability to give informed consent. Patients who on initial evaluation by the study investigator are deemed not to be capable of giving informed consent will not be evaluated further. Patients who are deemed capable of giving informed

consent will then be provided with a full and complete description of the study. Capacity will be determined by treating physician prior to the consent process. The capacity assessment will be a brief form checked and signed by the physician who is treating the subject. This form will be kept in the study chart of each subject. The patient will be provided with ample opportunity to review the consent and have all their questions addressed prior to completing enrollment. Written consent will be obtained prior to the commencement of study procedures.

Consent will follow IRB approved procedures. Consent will be obtained by the PI, [name], the study's MD, [name], and the study coordinator, [name]. Consent for patients will occur on the inpatient units of the Zucker Hillside Hospital at MRI.

In order to ensure that subjects understand the fundamental aspects of the study, we require that they demonstrate this by correctly answering a series of specific questions about the study covering key aspects of the study. These Study Information Reviews are IRB approved. The format of the Study Information Review is a question followed by two possible answers. The answers are written in a parallel sentence structure to minimize reading difficulty. We employ the parallel answer format instead of a true false format because of our experience that subjects with limited education and test taking skills better comprehend the parallel answer format.

An example of part of a Study Information Review is presented below.

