6.3 MEASURES TO MINIMIZE BIAS: RANDOMIZATION AND BLINDING

Patients who are willing to take part in the study and declining treatment by antipsychotic medication to sufficiently treat psychotic symptoms will be randomly assigned by the (trained) research coordinator to either sham or real rTMS following a permutation block randomization plan. The research coordinator

responsible for the randomization of patients, [name], will be unaware of what the next treatment assignment will be. Using this method of “concealed allocation of treatment assignment” ensures an unbiased randomization process. Double-blinding is ensured by the fact that the trained research assistant who is performing the rTMS treatments is not the same person (rater) who will conduct the psychopathology assessments. This way double-blinding is ensured in the sense that the rating is not influenced by the knowledge about the intervention arm (real or sham rTMS arm). This allows the unbiased assessment of changes in AVH severity due to rTMS without the prior knowledge of the rater whether the patient received real or sham rTMS. Patients declining medication will be randomly assigned to either the sham or the real rTMS group. For more detailed information on randomization see section 4.2.

For sham rTMS, the coil will be tilted by a 45-degrees angle. This procedure does not induce neuronal changes in the brain but still gives makes the characteristic noise produced during real rTMS stimulation.

Unblinding will only occur in the case of a serious adverse event or if patients wished to know after study completion in which study arm they have been. Unblinding will have to be approved by the PI first and can be done by the PI or the study coordinator.

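### Section 4.1 gives the randomisation list to the research coordinator, 6.3 says the coordinator who randomises cannot see the next assignment, and no available text separates the two or describes concealment

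*Combined protocol and SAP*

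**What the plan says.** Section 4.1 attaches three tasks to the title of research coordinator:

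- Assignment: patients "will be randomly assigned by the (trained) research coordinator to either sham or real rTMS".
- Custody of the list: "Copies of the resulting permutation blocks and randomization codes will be kept by the unblinded research coordinator". Only blinded personnel are barred from the codes.
- Communication: "the research coordinator will provide written notice of the randomization condition of the subject to the operator of the rTMS".

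Section 6.3 again has the trained research coordinator assign patients from a permuted-block plan. It adds that the coordinator responsible for this "will be unaware of what the next treatment assignment will be", and describes the arrangement as concealed allocation. It then says "For more detailed information on randomization see section 4.2". That section, "4.2 SCIENTIFIC RATIONALE FOR STUDY DESIGN", covers the blood sample and the choice of control group only.

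On timing, the schedule of activities (1.3) marks randomisation in the Screening column alone. Baseline assessment and the baseline MRI follow. Section 5.2 ties the pregnancy test to each MRI. Section 7.2 allows patients who are randomised but not treated to be replaced, and 9.3 limits the analysis to patients who completed both MRI and interview visits and all four sessions.

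**The concern.** Concealment protects the moment of entry. Anyone who can foresee the next arm, and who has a say in whether or when a patient enters, can shape the composition of the groups, deliberately or not. Analysis cannot reliably undo that, and it is hard to detect in a single-site trial of 40 patients. The separation of rater and rTMS operator in 4.1 and 6.3 is a real safeguard, but it protects the ratings and does nothing for entry.

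The timing point is a design matter, not a contradiction. A patient randomised at Screening can leave before the first session because of a positive pregnancy test, an MRI problem, a wish for antipsychotics or withdrawal of consent. That patient has been randomised but falls outside the 9.3 population. If randomisation came after baseline, the same departure would be a pre-randomisation loss and would not touch the comparison.

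**Working it through.** The plan states no figure on this point, so the main check is a comparison of the texts.

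**Step 1. Can 4.1 and 6.3 both be true?**

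- One coordinator: 4.1 places the blocks in that person's hands, so every upcoming assignment is visible. This contradicts 6.3.
- Two coordinators: both statements can hold, provided the list holder is not the assigner. The adjectives in 4.1 (unblinded for the holder, trained for the assigner) and the plural in 10.1.7 leave room for this. No available sentence states it.

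**Step 2. Is there a mechanism that would settle it?** Section 6.3 names concealment but mentions no envelopes, central service or independent holder. Section 4.2 has nothing on randomisation. Section 4.1 refers to a plan that the biostatistician will develop, which is not in the file.

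**Step 3. Would keeping the list from the assigner be enough?** Not by itself. Someone who knows past assignments and a fixed block size b (1:1) can predict with certainty an expected share 1/(b/2 + 1) of assignments. The plan gives no block size, so the range is assumed:

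| b | formula | share certain |
|---|---|---|
| 2 | 1/2 | 50% |
| 4 | 1/3 | 33% |
| 6 | 1/4 | 25% |
| 8 | 1/5 | 20% |

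With the list in hand the share is 100%.

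**Step 4. How long is the gap between randomisation and treatment?** Section 5.3 puts the MRIs on Days 1 and 3, so treatment is inferred to be Day 2.

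- Screening on Day 1: 1 day.
- Screening the day before Day 1: 2 days.
- Friday screening, Monday Day 1, Tuesday Day 2: 4 days.

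**Step 5. What might that gap cost?** The documents give no loss rate r. For illustration only, the number randomised to reach 40 treated is 40/(1 − r):

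- r = 5%: 40/0.95 = 42.1, about 2 extra.
- r = 10%: 40/0.90 = 44.4, about 4 extra.
- r = 20%: 40/0.80 = 50.0, 10 extra.

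**The case against.** The best defence is that two people are meant. A name is masked in 6.3, and section 10.1.5, listed in the contents as key roles and governance, is not in the text available here; either could separate the roles. That stands, and it rules out the stronger inference that concealment has failed. The wording of 4.1 and 6.3 and the wrong cross-reference would still need correcting.

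The route to selection is also thinner than the titles suggest. Under 5.5, patients are approached by participating psychiatrists or a research fellow (although 5.5 also speaks of trained study staff), and the treating physician judges capacity. Of consent, 5.5 says "Consent will be obtained by the PI", the study physician and the study coordinator. The research coordinator is not named there, and nothing equates that role with the study coordinator. So bias would need the list holder to influence entry or to pass on what the list shows.

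A reader might also infer that staff who obtain consent can see upcoming assignments, because 6.3 says "Unblinding will have to be approved by the PI first and can be done by the PI or the study coordinator". The documents do not support this. Section 6.3 limits unblinding to a serious adverse event or to a patient's request after study completion, which discloses one past assignment and not the next one.

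On timing, the evidence is one mark in a table read from PDF. The same table marks imaging at Screening, where the compensation table in 5.5 shows none. Section 8.1 requires screening on the day of inclusion or the day before, which fits the ordinary 1- to 2-day gap; the Friday case fits only if inclusion means enrolment. No differential loss by arm is shown. Section 8.1 would also carry the last observation forward for premature exits, which conflicts with 9.3 and needs its own resolution. These points limit how much can be claimed, but randomising after baseline avoids the early losses under any of these readings.

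**Conclusion.** The point holds as an unresolved inconsistency and a missing description. By role title, 4.1 defeats the concealment that 6.3 claims, and no available text repairs this. Selection bias at entry is possible; it is not shown, and the documents give no basis for a magnitude. The concern does not extend to bias in the ratings.

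The timing point is secondary and stands on the schedule as printed. The gap is about 1 to 4 days, assuming treatment on Day 2. The number lost in it is unknown; the 2, 4 or 10 above follow entirely from assumed rates and are not predictions. Moving randomisation removes only losses before the first session; later ones remain.

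The matter should be settled before recruitment, since concealment cannot be restored afterwards. Confidence is moderate because the missing role description could show that the roles are already separate.

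**What to change.** In 4.1, replace the sentence on custody of the blocks with wording such as: *The randomisation list is held by the study biostatistician (or another named role) who does not approach, consent or assign patients. Each assignment is released singly, only after the patient has been irrevocably entered, for example by opening the next sequentially numbered sealed envelope once the patient's number is written on it. Block sizes vary or are withheld from enrolling staff.*

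Also:

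- State by role who notifies the rTMS operator once the assignment is released.
- Point 6.3 to 4.1 instead of 4.2.
- In 1.3, move the randomisation row to after the baseline ratings, pregnancy test and baseline MRI, and before the first session. Section 6.1.2 already needs the baseline scan to locate the target, so this adds no new prerequisite for treatment.

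Envelopes are one option; any mechanism that keeps the list from those who enrol or assign would do. The cost is protocol wording, one schedule row and preparation of the envelopes with a named keeper who does not enrol patients. If envelopes are prepared in advance, the biostatistician need not be on call. The downside is slightly tighter logistics, because the assignment must be released between the baseline MRI and the first session.

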4.2 SCIENTIFIC RATIONALE FOR STUDY DESIGN

We will obtain a blood sample to assess the serum concentration of the antipsychotic at the moment of hospitalization to confirm that patients are antipsychotic-free thus eligible for this study. In the event of not having obtained a blood sample in the emergency room for an eligible patient that is willing to consent due to logistic reasons, we will obtain the specimen via venipuncture after the consent form is signed, provided that the patient did not receive antipsychotic drugs in the emergency room or inpatient unit. The specimens of individuals for whom an extra vial of blood was extracted for potential serum antipsychotic concentration analysis that later do not consent to participate in the study will be destroyed immediately without being processed.

For TMS, it is important to at least have a group that gets treated with the sham rTMS if no cross-over trial is possible and no waiting-list is planned to be included in the study.

Having matched patients in the control group compared to the treatment group allows a comparison of the two in terms of symptoms. A healthy control group would not allow such a comparison.

